9.3 POPULATIONS FOR ANALYSES

The **analysis population** is limited to subjects who meet intervention eligibility requirements at an index visit. We will use data from the Wizard algorithm runs outside the encounter at 6 and 12 months post-index visit to analyze the impact of the intervention on adherence (e-PDC) and clinical outcomes (A1C, BP, statin use). The cost analysis is limited to the subset of these patients who have HealthPartners insurance for at least 11 of 12 months after the index visit.

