 Impact of the intervention on overall healthcare costs Predicted long- term health impact and cost- effectiveness of the intervention from the health system (payer) perspective 	 We will measure the cost of delivering the intervention using micro-cost accounting methods and the incremental medical care costs attributable to the intervention, defined from the health system perspective, measured using insurance claims incurred in the median 12-month pre- and post- index date periods by participants with an affiliated HealthPartners insurance plan in each study group. We will use a cardiovascular disease microsimulation model to predict the impact of the intervention on health outcomes and its cost- affective and defined from the 	 If the intervention is found to be effective, the cost of delivering the intervention and its incremental effect on medical care utilization will be important outcomes to informing dissemination and implementation to other systems and settings. A full measurement of the value of the intervention cannot be observed during the study period, but validated microsimulation methods can be used to estimate the full impact of the intervention on preventing or delaying incidence of disease and in averting future medical care costs—both of which will be important to inform the
	effectiveness, defined from the health system perspective, over up to a 30-year prospective time horizon.	translation and adoption of the intervention, if found to be effective.
Tertiary/Exploratory	health system perspective, over up to	translation and adoption of the

	OBJECTIVES		ENDPOINTS	JUSTIFICATION FOR ENDPOINTS
	What are we			
			How are we measuring it?	
	measuring			
1.	The impact of the	1.	We will assess reduction in 10-	The CDS assesses and prioritizes CV
	intervention on		year CV risk measured at each	risks factors according to the
	10-year CV risk		encounter	percentage of 10-year CV risk that
2.	Survey assessed	2.	We will conduct phone surveys	can be reduced if actions are taken
	patient reported		on a random sample of up to	to address the risk factor.
	adherence		1400 eligible patients	
З.	Patient and		approximately 2-4 weeks after an	Provider and patient experience and
	provider		index visit and subsequently ~6	satisfaction information provide end-
	experience and		months later (after a phone	user opinions of the intervention
	satisfaction		outreach has occurred)	which helps to assess impact and

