4.2 SCIENTIFIC RATIONALE FOR STUDY DESIGN

This trial was originally conceived and approved as a clinic cluster randomized trial of control (usual care) versus intervention. However, the intervention was suspended in March 2020 after one week of implementation due to COVID-19 pandemic response that resulted in loss of the separation of treatment groups. There were clinic closures, decreased office visits, and increase in telehealth care. To address concerns related to patient crossover from intervention to control settings (and vice versa) in the ongoing COVID-19 era, the study was transitioned to a patient level randomization that was conducted using a computerized allocation by the CDS at the time of an index visit within any of the 28 study clinics. The main advantage to the patient level randomization is that no matter what happens with clinics closing and opening, provider moving between clinics, and where video encounters take place, the study subjects consistently receive the ReachOut intervention or usual care without crossover. Additionally study power increases with the patient-level design compared to a clinicrandomized design. The disadvantage to the patient level randomization design, and why it wasn't the initial choice when the grant was originally funded, is concern over clinician contamination due to a potential learning effect from the intervention that translates to control patients. However, the net effect of this contamination would be a reduction in the intervention effect which would not undermine conclusions if the intervention is found to be effective. Given how the clinical setting changed abruptly and unexpectedly due to the COVID-19 pandemic, the advantages of a patient-level study design were determined to outweigh the disadvantages and be the most appropriate way to complete the study and test the hypotheses.

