5.2 EXCLUSION CRITERIA

An individual who meets any of the following criteria will be excluded from the study analysis:

- 1. Patients enrolled in hospice,
- 2. Patients with active cancer or undergoing chemotherapy
- 3. Patients with pregnancy identified in the last year
- 4. Patients without HealthPartners insurance coverage for at least 30 continuous days in the 12 months before or 12 months after the index visit will be excluded from the cost analysis.
- 5. For Statin cohort, most recent LDL result <100 mg/dl in the last 2 years

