6.3 MEASURES TO MINIMIZE BIAS: RANDOMIZATION

Patients are randomly allocated 1:1 through a computer-generated program to either control or intervention. Contamination across intervention arms is unlikely because all patients receive CDS interventions based on their arm assignment. All patients assigned to the study arms are analyzed based on their arm assignment.

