7.3 LOST TO FOLLOW-UP

All eligible patients who are enrolled in the analysis at an index visit will be included in the analysis (unless they have opted out of research). Patients who move, disenroll from the clinic, or have no follow up in the clinic will be accounted for through the analytic plan. We anticipate loss to death < 2% and disenrollment from the insurance plan in < 5% per year. Patients who have opted out of research per federal law are excluded from the analysis (<2%). Few patients transfer care between HealthPartners and/or Park Nicollet clinics.

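### The cost analysis has unreconciled insurance-coverage rules, and the section 9.3 rule selects patients on coverage after randomization

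*Combined protocol and SAP*

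**What the plan says.** Three places define who enters the cost analysis.

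- Section 9.3 limits it to patients with "HealthPartners insurance for at least 11 of 12 months after the index visit". It sets no condition on the period before index.
- Section 5.2, exclusion 4, removes from it "Patients without HealthPartners insurance coverage for at least 30 continuous days in the 12 months before or 12 months after the index visit".
- Section 3 measures incremental medical costs from claims of "participants with an affiliated HealthPartners insurance plan in each study group", with no minimum duration.

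Section 4.2 describes allocation as "conducted using a computerized allocation by the CDS at the time of an index visit", so any coverage after index is observed after randomization. Section 6.3 says patients are analyzed in their assigned arm. Section 7.3 says eligible patients enrolled at index are included unless they opted out of research. On losses, section 7.3 says "We anticipate loss to death < 2% and disenrollment from the insurance plan in < 5% per year", and also "Patients who move, disenroll from the clinic, or have no follow up in the clinic will be accounted for through the analytic plan".

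The cost model in section 9.4.3 is a generalized estimating equation, typically gamma with a log link, adjusted for demographics and baseline risk. It mentions no person-time, censoring weight or treatment of death. The methods named under Missing Data in section 9.4.2 are for A1C, SBP and the adherence hypotheses, not for cost.

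**The concern.** Two issues arise. First, two analysts following different sections would build different datasets for H2.1, and nothing in the plan stops that choice from being made after costs have been seen.

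Second, H2.1 compares 12-month costs by randomized assignment, but the 9.3 rule keeps only patients who stay alive and insured for about 11 months. The two arms of that subset need not be comparable, and this departs from the principle of analysis by assignment in sections 6.3 and 7.3. The 12-month incremental cost, and any cost-effectiveness result that uses it, would rest on that subset.

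**Working it through.** The documents give no sample size, power or insured fraction for the cost analysis, so there is no planned figure to reproduce. The check has three steps.

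**1. Do the rules agree under any reading of section 5.2?**

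| Reading of 5.2 | After index | Before index | Against 9.3 |
|---|---|---|---|
| Literal: 30 continuous covered days are enough | 30 days, or possibly none if coverage before index qualifies | Can qualify a patient by itself | Far looser |
| Gap: 30 or more uncovered days exclude | Close to 11 of 12 months | Same condition applies | Adds a pre-index condition that 9.3 lacks |

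They disagree under both. The pre-index difference matters because sections 3 and 9.4.3 measure costs in the 12 months before index. A patient insured only from the index date meets 9.3 but has no earlier claims from the plan.

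**2. How many patients does the 9.3 rule remove?**

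Inputs, from section 7.3: death 2% and plan disenrollment 5% per year, both stated as upper limits. Assumptions: constant, independent hazards, and the death figure taken as annual.

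- Combined hazard: h = −ln(0.98) − ln(0.95) = 0.0202 + 0.0513 = 0.0715 per year.
- Lost by time t (in years): 1 − exp(−h·t).
- By 12 months: 1 − 0.98 × 0.95 = 6.9%.
- By 11 months, dropped under 9.3: 1 − exp(−0.0715 × 11/12) = 6.3%.
- By 30 days, dropped if the literal 5.2 rule is applied after index: 1 − exp(−0.0715 × 30/365) = 0.6%.
- Classified differently by those two rules: about 5.8%.

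At half the ceilings (1% and 2.5%) the figures are 3.5%, 3.2%, 0.3% and 2.9%.

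**3. What could this do to the arm contrast?**

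Let stayers have the same mean cost in both arms, so that the completers-only ratio is 1.00. Let leavers cost k times stayers (assumption), with shares f_I and f_C dropped in intervention and control. Then

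true ratio = [1 + f_I(k − 1)] / [1 + f_C(k − 1)].

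- Equal shares and equal k: the ratio is 1.00 for every k, so there is no bias.
- f_I = 5.4%, f_C = 7.4% (a 2-point gap, assumed):
  - k = 2: 1.054/1.074 = 0.981
  - k = 3: 1.108/1.148 = 0.965
  - k = 5: 1.216/1.296 = 0.938
- The same gap in the other direction with k = 3: 1.148/1.108 = 1.036.

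The documents do not indicate the direction or the size of any gap.

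**The case against.** The strongest reply is that sections 5.2 and 9.3 can be applied together, one as an exclusion and the other as a restriction. Section 9.3 then governs the period after index. This stands against one stronger inference a reader might draw: that a patient with a single covered month enters with one month of claims counted as a year's cost, an understatement of up to 11/12. That happens only if 9.3 is ignored, and section 9.4.3 also draws costs from clinical encounter data. Applying both rules does not settle the pre-index condition, however, and it leaves the selection after randomization in place.

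Three other strong readings are tempting and not supported.

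- That both rules select after randomization. Section 5.2 says "for at least 30 continuous days in the 12 months before or 12 months after the index visit", so coverage before index may be enough. Only 9.3 clearly selects on later coverage.
- That costs are biased downward because end-of-life costs disappear. If 2% die at 3, 5 or 10 times others' cost (multiples with no source in the documents), leaving them out lowers the mean by 1 − 1/(0.98 + 0.02k) = 3.8%, 7.4% or 15.3%. Those are shifts in a mean level, whereas H2.1 is a contrast between arms. Section 9.4.3 also leaves out emergency and inpatient costs unless they differ significantly, and section 5.2 already excludes hospice and active cancer, so large multiples fit this cost measure poorly.
- That the randomized comparison is broken. With equal loss and equal cost multiples the ratio is unbiased. Covariate adjustment may reduce imbalance between the retained arms, though it cannot be relied on to remove selection.

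It is also fair that expected loss is below 7% and that this is a secondary analysis.

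**Conclusion.** The coverage rules conflict, and the conflict survives either reading of section 5.2. Section 9.3, followed as written, conditions a by-assignment comparison on coverage after randomization, and the plan gives no method for death or disenrollment in the cost model. About 6% of insured patients would be dropped at the section 7.3 ceilings, and about 3% at half those rates, assuming constant hazards.

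Bias in H2.1 is possible but not established. It requires loss, or leavers' costs, to differ by arm. A 2-point gap in loss with a threefold cost multiple, both assumed, moves the ratio by about 3.5%. The point is confined to the secondary cost result and any cost-effectiveness figure that uses it. The Aim 1 endpoints are untouched. It should be corrected before the cost data are analyzed.

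**What to change.** - State one coverage rule, worded identically in sections 3, 5.2 and 9.3, and fixed at or before index. For example: covered on the index date, plus whatever pre-index minimum the sponsor needs for baseline costs. A longer minimum gives fuller baseline claims but excludes newly insured patients.
- Keep every randomized patient who meets that rule in the assigned arm. Exclusion for events after index then falls to zero.
- Count death as complete follow-up, with costs as accrued. Treat disenrollment as censoring, with inverse-probability-of-censoring weights. Do not use an offset for covered months, because it would extrapolate a decedent's costs to a full year.
- Report death and disenrollment by arm.
- Keep the 11-of-12-months-after subset as a sensitivity analysis.

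The cost is revised wording in three sections and a slightly more complex cost model. No new data collection is apparent, since enrollment, claims and encounter data are already part of the plan.

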9.4 STATISTICAL ANALYSES

The primary predictor is the study arm to which a patient is randomized. This variable is a one-degreeof-freedom contrast with the control group as the reference category and adherence intervention as the other category. Patient and provider characteristics will be documented in order to assess the extent to which results apply to subgroups of patients. Patient characteristics obtained from the EMR include demographics, health care payer, and comorbid conditions. We will have complete information for physician characteristics, including age, years since graduation, sex, full- or part-time work status, and physician or allied provider (e.g., nurse practitioner). Pharmacist characteristics will be collected by survey.

9.4.2 ANALYSIS OF THE PRIMARY EFFICACY ENDPOINT(S)

Definitions of Dependent Variables (Aim 1): The primary dependent variables are described in Table 3 below.

Table 2. Description of Dependent Variables Used in Primary and Secondary Analysis.						
Variable	Description	Data Source	Classification			
PDC provided in	For each condition, achievement of e-PDC ≥80%	EMR	Binary			
the EMR (H1.1a,	for all medication classes for that particular					
H1.2a, H1.3)	condition (diabetes, hypertension, statin					
	indication) in the 12 months following index date.					
BP reduction Mean change in SBP from the last BP within the EMR vitals Contir		Continuous				
(mmHg) (H1.1b) 12 months prior to the index visit, to the last BP						
	value within 12 months after the index visit.					
Change in A1C Change in A1C value from the last lab test within EMR Continue		Continuous				
value (H1.2b) the 12 months prior to the index visit, to the last procedure						
	lab test within 12 months after the index visit.	results				

Drug-specific PDCs are extracted from Epic EMR. Key secondary dependent variables (also defined in Table 3) include (a) total 10-year ACC/AHA CV risk, and (b) other objective measures of medications adherence such as PDC calculated using claims data, and (c) survey assessed patient self-reported adherence using a validated instrument.¹¹⁰ We will assess additional dependent variables through a patient survey including barriers to adherence,¹¹¹ shared decision making,¹¹² health care satisfaction,¹¹³ and provider and pharmacist knowledge, attitudes, beliefs, and satisfaction with the CDS. **Analysis Plan for Aim 1 (Adherence and Outcome Hypotheses)**: Hypotheses H1.1a, H1.2a, H1.3 posit that patients assigned to the adherence intervention will be more likely than patients assigned to usual care to have high medication adherence (e-PDC ≥80%) in the 12 months following the index visit for BP medications (H1.1a), glucose medications (H1.2a), and statin medications (H1.3). Generalized linear model (GLM) regression with a logit link and binomial error distribution will be used to test the effect of the intervention. The general form of the analytic primary model for testing medication adherence is: $logit(Pr[PDC \ge 0.8]) = \beta_0 + \beta_1(Intervention) + \beta_c(Covariates)$

The dependent variable in each model (antihypertensive medications, glucose-lowering medications, statins) is a binary indicator of high medication adherence (e-PDC \geq 80%) and is predicted by a binary indicator of adherence intervention assignment. We will screen and include patient characteristics in the model when they are unbalanced by treatment arm. In supplemental analyses, we will extend the GLM approach described above by including random intercepts to evaluate potential clustering effects at the level of clinic and/or provider.

H1 will be supported if the intervention group effect β_1 is significant and positive, supporting the prediction that clinical encounters with the adherence intervention are more effective than encounters without them for increasing medication adherence. Treatment group heterogeneity by patient sex, age group, race, insurance class, and comorbidity count will be assessed by including interaction terms consisting of products of patient variables and the intervention indicator.

Hypotheses H1.1b and H1.2b posit that patients assigned to the adherence intervention will be more likely than control patients to have reduced SBP (H1.1b) and reduced A1C (H1.2b) in the 12 months following the index visit.

 $E(Y)_t = \beta_{00} + \beta_{10}(Intervention) + \beta_{01}(Time) + \beta_{11}(Intervention * Time) + \beta_{c0}(Covariates)$ The analytic model will be a generalized linear model with an identity link and normal error distribution. The dependent variable Y (SBP for H1.1b and A1C for H1.2b) is predicted by a binary indicator of intervention assignment, time (pre-intervention vs. post), and the interaction of intervention assignment and time. We will screen and include patient characteristics in the model when

they are unbalanced by treatment arm, and will evaluate the potential for clustering by clinic and/or provider. A significant intervention group-by-time interaction term (P < 0.05) and a pre-specified contrast

A significant intervention group-by-time interaction term (*P*<0.05) and a pre-specified contrast indicating more reduction in SBP (H1.1b) or A1C (H1.2b) in the intervention than the control arm will support the prediction that encounters with the adherence intervention are more effective than encounters without it for improving BP and glycemic clinical outcomes.

Missing Data: All key analytic variables will be derived from EMR or health plan databases in which it is extremely rare for care-delivery information to be incompletely recorded. The primary endpoints for differential change in A1C and SBP by study arm will be analyzed using all available data at multiple time periods using direct likelihood-based ignorable methods obtained via generalized linear models, with no need to model the missing data process, and will yield valid inference when the outcome is missing at random.^{114,115} For H1.1a, H1.2a, H1.3, if preliminary analyses determine that patient covariates are predictive of missing outcome data, we will consider using one or more of the following strategies. We will include these variables as covariates so that the model is conditioned on these characteristics. We will assume that missing values represent failed trials (e.g., a failure to realize one of the binary outcomes), resulting in conservative estimates of intervention effects. Finally, multiple imputation procedures may be employed to accurately estimate parameters across multiple imputed data sets.

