1 PROTOCOL SUMMARY

1.1 SYNOPSIS

Title:	A Team-Based and Technology-Driven Adherence Intervention to Improve Chronic Disease Outcomes
Study Description:	More than 50% of adults treated for diabetes, hypertension, or lipid disorders have suboptimal medication adherence, a prominent barrier to continued improvement in chronic disease care in the United States. Primary care providers (PCPs) often fail to identify medication nonadherence and/or have insufficient time and training to address underlying reasons for it. In this project, we propose a patient-centered and technology-driven strategy to identify patients with adherence issues and apply a team approach that will help them achieve evidence-based personalized goals for glucose, blood pressure (BP), or lipids. The study is a two-arm pragmatic patient randomized trial at 28 primary care clinics targeting adult patients not meeting recommended goals for BP, A1C, or statin use with poor medication adherence.
Objectives:	 (1) Identify and address nonadherence for adults with chronic diseases; (2) Improve management of previously uncontrolled blood pressure, blood sugar, and lipid disorders; and (3) Increase patient involvement in medication decision making.
Endpoints:	Primary Endpoint: (a) For each condition, achievement of an Epic generated proportion of days covered (e-PDC) \geq 80% for all medication classes for that particular condition (diabetes, hypertension, statin indication) in the 12 months following index date. (b) Mean change in systolic blood pressure (SBP) from the last BP within the 12 months prior to the index visit, to the last BP value within 12 months after the index visit. (c) Change in A1C value from the last lab test within 12 months prior to the index visit to the last lab test within 12 months prior to the index visit to the last lab test within 12 months prior to the index visit to the last lab

Study Population:	Secondary Endpoints: cost and cost effectiveness of the intervention. Tertiary Endpoints: (a) total 10-year American College of Cardiology/American Heart Association (ACC/AHA) Cardiovascular (CV) risk, (b) patient reported medication adherence using a validated survey instrument, (c) Patient and provider experience and satisfaction, (d) facilitators and barriers to implementation of the intervention The study includes adult patients from at least 28 HealthPartners Medical Group (HPMG) primary care clinics (HealthPartners (HP) and Park Nicollet (PN) in Minnesota.
Phase:	3

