3 OBJECTIVES AND ENDPOINTS

OBJECTIVES	ENDPOINTS	JUSTIFICATION FOR ENDPOINTS
What are we	How are we measuring it?	
measuring		
Primary		
1. Impact of the	1. We will assess patient achievement	The e-PDC has been operationalized
intervention on	of (a) an e-PDC ≥80% for all BP	by the Epic (Epic Systems
blood pressure	medications and (b) a reduction in	Corporation) and made readily
medication	systolic BP. (Time Frame is 12-month	available in their 2018 EMR version.
adherence and	period after an index office visit.)	This e-PDC is available for

OBJECTIVES	ENDPOINTS	JUSTIFICATION FOR ENDPOINTS
What are we	How are we measuring it?	
measuring		
systolic blood pressure control	2. We will assess patient achievement of (a) e-PDC≥80% for all non-insulin	prescription medication and provides current levels of adherence as well as a measure of the quality of data used
2. Impact of the intervention on non- insulin glycemic medication adherence and A1C control	 glycemic medications and (b) a reduction in A1C values. Time Frame is 12-month period after an index office visit. 3. We will assess patient achievement of an e-PDC ≥80% for a statin 	to calculate the score expressed as the confidence level. The e-PDC reduces overestimation of adherence, eliminates potential recall bias associated with patient self-report, and provides a conservative estimate of the highest
3. Impact of the intervention on statin medication adherence	medication. (Time Frame is 12- month period after an index office visit)	possible level of medication consumption per the available data at the moment.
		Systolic blood pressure, A1C, and statin use are intermediate variables strongly associated with morbidity and mortality related to the associated clinical domains.
Secondary		

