5 STUDY POPULATION

5.1 INCLUSION CRITERIA

To be eligible for the study, the patient must have an office visit with a clinician (physician or advanced practice provider) within a primary care department (family medicine, internal medicine, combined pediatric/internal medicine) at one of the 28 study clinics within the HealthPartners Medical Group or Park Nicollet care system, and meet all of the following criteria:

1. Age 18 to 75 years, inclusive. The evidence-based guidelines on which the CDS intervention is based are not applicable outside this age range.⁹¹

2. Have a primary care encounter (index visit) at a selected clinic.

3. Have a primary care encounter that meets one of or more of the following clinical criteria for care goals and medication adherence:

 In the 12 months prior to the index visit, most recent A1C ≥8% AND have one or more active non-insulin glycemic medications on their EMR medication list AND a potential adherence issue for one or more of these medications based on the Epic Medication Adherence score (e-PDC <80%, moderate or high confidence)

- Two consecutive encounters with BP values ≥140/90 mm Hg AND one or more BP medications on their EMR medication list AND a potential adherence issue identified (e-PDC <80%, moderate/high confidence)
- 3. Meet the ACC/AHA criteria listed below for moderate or high-intensity statin use AND a statin medication on their EMR medication list AND a potential statin adherence issue identified (e-PDC <80%, moderate/high confidence):
 - a. Age >21 with atherosclerotic CV disease identified by a CVD diagnosis on the problem list or two or more ICD-10 diagnostic codes in the last 2 years
 - b. Aged >21 and LDL >190 mg/dl
 - c. Aged 40 to 75 AND diabetes identified by the diagnosis on the problem list or two or more ICD-10 diagnostic codes in the last 2 years
 - d. Aged 40 to 75 with 10-year CV Risk Score 7.5% based on the ACC/AHA 10-year ASCVD risk equation.

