9 STATISTICAL CONSIDERATIONS

9.1 STATISTICAL HYPOTHESES

• Primary Efficacy Endpoint(s):

For patients 18 to 75 years old not at goal for BP, A1C, or statin use and with medication nonadherence, those randomly assigned to the ReachOut Adherence Intervention will have improved adherence and clinical outcomes compared to those randomly assigned to control.

Hypothesis 1.1 Relative to those assigned to control, eligible adults with uncontrolled BP and baseline nonadherence to one or more BP medications who are assigned to intervention will be more likely to achieve (a) an e-PDC \geq 80% for all BP medications and (b) a reduction in systolic BP in the 12-month period after the index visit.

Hypothesis 1.2 Relative to those assigned to control, eligible adults with diabetes and A1C \geq 8% and baseline nonadherence to a non-insulin glycemic medication who are assigned to intervention will be more likely to achieve (a) e-PDC \geq 80% for all non-insulin glycemic medications and (b) a reduction in A1C values in the 12-month period after the index visit.

Hypothesis 1.3 Relative to those assigned to control, eligible adults with inadequately managed lipid disorders with baseline non-adherence to a statin who are assigned to intervention will be more likely to achieve an e-PDC \geq 80% for a statin in the 12-month period after the index visit.

• Secondary Efficacy Endpoint(s):

Assess the cost and cost-effectiveness of the ReachOut Adherence Intervention from the health system (payer) perspective through empirical analysis and microsimulation modeling of patient utilization and disease outcomes.

Hypothesis 2.1: Relative to those who are assigned to control, eligible study subjects who are assigned to intervention will have significantly higher overall health care costs in the 12-month period following the index visit, after controlling for demographics and baseline clinical risk factors.

Hypothesis 2.2: Relative to those who are assigned to control, eligible study subjects who are assigned to intervention will have significantly lower overall resource use and fewer major CV and diabetes-related events in a 30-year post-intervention simulated analysis using cost-effectiveness microsimulation modeling methods.

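### The primary diabetes adherence endpoint (H1.2a) is defined two ways: non-insulin drugs only in Sections 3 and 9.1, all diabetes medication classes in the synopsis and Table 2

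*Combined protocol and SAP*

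**What the plan says.** Four places tie the diabetes measure to non-insulin drugs.

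- Section 3, objectives and endpoints table: achievement "of (a) e-PDC≥80% for all non-insulin" glycemic medications.
- Section 9.1, Hypothesis 1.2: e-PDC of at least "80% for all non-insulin glycemic medications and (b) a reduction in A1C values in the 12-month period after the index visit".
- Section 5.1, diabetes entry criterion: patients must "have one or more active non-insulin glycemic medications on their EMR medication list AND a potential adherence issue for one or more of these medications".
- Section 9.2: the H1.2 cohort is counted as patients with A1C of 8% or more and at least one non-insulin glucose drug at e-PDC below 80%.

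Three places carry no such limit.

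- Section 1.1, synopsis, primary endpoint (a): e-PDC of at least "80% for all medication classes for that particular condition (diabetes, hypertension, statin indication) in the 12 months following index date".
- Section 9.4.2, Table 2, the row labelled H1.1a, H1.2a and H1.3: the same rule, "for all medication classes for that particular" condition.
- Section 9.4.2, analysis text: H1.2a is restated as concerning glucose medications, and the model outcome is introduced with "The dependent variable in each model (antihypertensive medications, glucose-lowering medications, statins".

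Insulin use is not among the exclusions in Section 5.2.

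**The concern.** Insulin is a diabetes medication class, so the synopsis and Table 2, taken at their word, include it, while H1.2a leaves it out. Section 9.4.2 says that drug-specific values are extracted from Epic, so someone has to decide which drugs enter the all-drugs rule. No passage says which wording governs. Two careful programmers could therefore derive two different primary endpoints from the same records.

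Two things are at stake. First, an undeclared choice between two versions of a primary endpoint could be made after the data are seen. Second, if insulin is scored, some patients who succeed on the drugs that the hypothesis names would be counted as failures. That lowers the success rate in both arms and shrinks the absolute difference between them.

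**Working it through.** **1. Who changes status.** Take a patient with metformin e-PDC 60% at index. At 12 months metformin is 90% and insulin is 55%. Under H1.2a this is a success; under Table 2 read literally it is a failure. With metformin 90% and insulin 85%, or with no insulin, both rules give success. With metformin 70%, both give failure. So a patient changes status only if every non-insulin drug reaches 80% and insulin does not, or if insulin e-PDC is missing and counted as failure. The missing-data text in 9.4.2 lists counting missing values as failures among its options.

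**2. The plan's own figure.** Inputs from Section 9.2: control 50.0%, intervention 59.9%, two-sided α = 0.05, power 80%, 1:1 allocation, N = 832.

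- Uncorrected n per arm = [1.960·√(2p̄(1−p̄)) + 0.842·√(p₁(1−p₁)+p₂(1−p₂))]² / (p₂−p₁)², with p̄ = 0.5495. This is (1.960×0.7036 + 0.842×0.7001)² / 0.099² = 395.3, so 396 per arm and 792 in total.
- Continuity-corrected n per arm = (395.3/4)·[1 + √(1 + 4/(395.3×0.099))]² = 415.3, so 416 per arm and 832 in total. This matches the plan exactly.
- Uncorrected power at 416 per arm = Φ[(0.099×√416 − 1.960×0.7036)/0.7001] = Φ(0.914) = 82%. This is the baseline for step 3.

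None of these inputs involves insulin.

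**3. Possible dilution (assumptions, not figures from the documents).** Let f be the share of the cohort on insulin. Let g be the chance that an insulin user who succeeds on the non-insulin drugs also has insulin e-PDC of at least 80%. Take g as equal in both arms, and insulin use as unrelated to success on the other drugs. Both success rates are then multiplied by k = 1 − f + fg, and a share f(1−g) of H1.2a successes is rescored as failure. Power is uncorrected, at 416 per arm.

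| f | g | k | Control vs intervention | H1.2a successes rescored | Power |
|---|---|---|---|---|---|
| 0% | – | 1.000 | 50.0% vs 59.9% | 0% | 82% |
| 10% | 70% | 0.970 | 48.5% vs 58.1% | 3% | 79% |
| 20% | 60% | 0.920 | 46.0% vs 55.1% | 8% | 75% |
| 35% | 50% | 0.825 | 41.2% vs 49.4% | 17.5% | 66% |
| 50% | 40% | 0.700 | 35.0% vs 41.9% | 30% | 54% |
| any | 100% | 1.000 | 50.0% vs 59.9% | 0% | 82% |

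**4. Insulin started after index.** Suppose insulin starts at month 9. Its fills can cover at most 3/12 = 25% of a 12-month window, or 3/6 = 50% of the six-month default that Section 2.2 gives for the Epic measure. Both are below 80%, but only if days before the first fill count in the denominator. The documents do not say whether they do, so this case cannot be scored with certainty under Table 2. Under H1.2a the question does not arise for insulin.

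**The case against.** The strongest reply is that the Table 2 row is a generic line covering three conditions and is labelled with H1.2a. Section 9.1 writes H1.2a out with the non-insulin limit, and Section 9.2 repeats that limit in the patient count. An analyst following the label would reach the narrower rule, and no passage says that insulin e-PDC will be scored. This stands in part: Table 2 cannot be called the rule that will certainly be applied. It does not remove the conflict, because 9.4.2 restates H1.2a in its own text without the limit and the synopsis has no cross-reference to fall back on.

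Four stronger readings are tempting but not supported.

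- *Insulin users fail H1.2a.* They can fail but need not; step 1 shows who changes status.
- *The power statement in 9.2 is broken.* It reproduces exactly for the non-insulin endpoint. Its N of 832 is also a deliberate halving of the projected 1,664. At 1,664 the 20%, 35% and 50% insulin rows would have about 96%, 92% and 83% power.
- *The arms are compared unfairly.* Randomisation balances insulin use at index in expectation. Insulin started later could differ by arm, since pharmacists may change medications under protocol (Section 6.1.1), but the documents do not show that it would.
- *The losses in the table are estimates.* Insulin use and insulin e-PDC appear nowhere in the documents. If adherence to insulin and to the other drugs is positively correlated, g is higher among those who succeed on the other drugs and the loss is smaller.

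**Conclusion.** The point holds as a conflict between two stated rules for one primary endpoint. Sections 3 and 9.1 exclude insulin; the synopsis and Table 2, read literally, include it; and insulin co-users can enter the trial. If the literal rule were coded, some H1.2a successes would become failures on a drug class outside the hypothesis.

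The size is unknown. Under the assumptions shown, power ranges from 82% (no loss) to 54%, and a milder mix gives 79%. The supported consequence is an ambiguous endpoint with possible dilution. The sample-size calculation stands for the non-insulin endpoint. Because this is a primary endpoint, the wording should be settled before outcome data are examined.

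**What to change.** In the synopsis, in Table 2 and in the 9.4.2 analysis text, state the diabetes endpoint as e-PDC of at least 80% on all non-insulin glycemic medications. Add one sentence that insulin e-PDC is not scored, whether insulin is on the list at index or started later. Insulin use by arm can be reported descriptively.

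The cost is a wording change in those three places and one drug-class filter in the derivation program. No new data are needed, and N = 832 and 50.0% vs 59.9% are unchanged. The filter does not settle how a non-insulin drug added during follow-up is counted; that needs its own sentence.
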